These design group activities will enable us to refine and finalize *CWB-LIVE* content and synchronous/ asynchronous delivery strategies. We will work with our instructional design specialists to finalize the look, feel, and flow of the course, embed it on the learning management platform (i.e., Canvas), and produce an accompanying caregiver manual and other associated course materials (e.g., workbook, reflective journal, and course completion guide). The instructional design team will record any additional video assets – likely brief (4-8 minute) minitalks provided by our team and other experts as well as collaborating Black caregivers – that will introduce and reinforce the text and pictorial content of the course that was identified as missing from the original course. Based on previous experience, video production should take no more than three weeks, then editing and integrating these materials into the revised course format should take no more than three weeks.

Aim 2. (Months 10-24) Assess the feasibility, usability, acceptability, and preliminary efficacy of the prototype *Caregiving while Black-LIVE* course. We will employ a mixed-methods pre-post no control design to gather formative and evaluative data from four cohorts (n=10 each) of Black caregivers. We will gather preliminary efficacy data on caregiving mastery, health literacy, and emotional well-being (i.e., stress, anxiety, and burden).

Design & Procedures. Accessing the recruitment resources identified above, we will recruit 40 Black caregivers in four cohorts of 10 each to participate in the prototype test. Caregiver Inclusion Criteria: (a) at least 18 years of age; (b) family member (or friend) who self-identifies as Black American and as the principal caregiver of a community-dwelling PLWD (not in hospice care) and who is the principal companion of that person during healthcare encounters; (c) provides some hands-on care multiple times a week; (d) has access to an electronic device and/or access to broadband internet; and (e) able to speak and understand English. Caregivers are not required to be co-located with the care recipient. Caregiver Exclusion Criteria: (a) has plans to relinquish caring responsibilities for PLWD; or (b) considering moving the PLWD to an institutional setting within the next 6 months.

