Data Collection & Management. Using established instruments, we will collect data on participants' self-efficacy (mastery; 6- scales, 3-6 items, α =.71-.92), 42 stress (14-item; α =.88), 43 depression (20-item; α =.90), 44 anxiety (20-item; α =.95), 45 burden (22-item; α =.91), 46 health literacy (9 subscales; 4-6 items, α =.80), 47 and, at baseline, their reasons for caregiving (10-item, α =.86), 13 and experience of medical discrimination (8-item; α =.89) 48 through 30-minute phone/video interviews. A separate, team-developed evaluation questionnaire, to be administered at week 12 through REDCap, will assess issues of course acceptability and utility and participants' sense of benefit. Aim 2 baseline and follow-up instrument-based quantitative data and Exploratory Aim 3-month quantitative data will be gathered through interviews conducted by phone or videoconference by an interviewer trained and supervised by Co-I [name]. At the time of each interview, quantitative data will be entered directly into a dedicated project tablet computer and saved on Emory's secure REDCap platform set up to include, where possible, data delimiters to ensure correctness and minimize missing data. Data will be exported weekly and analyzed for data cleaning and verification. Upon completion of each cohort data-gathering point, all data will be merged for scale computation, aggregation, and analysis.

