Data Analysis Plan. Descriptive statistics and frequency distributions will be examined to identify outliers and ensure integrity of all data. For all multi-item scales, internal consistency will be examined using Cronbach's alpha and associated statistics (e.g., item-total correlations, alpha if item deleted). To determine the feasibility of collecting data on caregiving well-being measures for a subsequent clinical trial, preliminary analyses will examine baseline differences among completers and non-completers using 2-group comparison tests (t-tests and non-parametric equivalent tests for continuous variables (normally or non-normally distributed) and Chi-Square tests for categorical variables). The association of predisposing factors (demographics, caregiver history, relationship and care recipient status at baseline) with changes in outcomes over time will be examined to identify potential covariates. Where significant associations with baseline measures are detected, these potential confounders will be controlled for in subsequent analyses using covariate model adjustments. We will use multilevel longitudinal modeling analysis to test for significant changes over the 3 time points from baseline to 2- and 12-weeks post course completion. Given an expected final sample size of 36 (assuming 10% attrition to reduce threats to validity)⁴⁹ with data completed at the 3 time points, we will be powered at 80% power and 5% level of significance to detect a large effect size (Cohen's f = 0.53) for changes from baseline.

The post-course qualitative interviews will be analyzed under the direction of PI [name] and provide information about the feasibility, usability, and acceptability of course material and overall course

Page 9 of 32 Version: 1_05/05/2023

synchronous/asynchronous design. Three other sources of information will contribute to our ability to move forward with the preparation of a revised course. The faculty-moderated sessions will

Activities		Year 1				Year 2			
Phase 1		Qtr 2	Qtr 3	Qtr 4	Qtr 1	Qtr 2	Qtr 3	Qtr 4	
IRB approval; hire and train staff	Х								

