We will provide \$40.00 gift cards (e.g., Amazon card) to participants for each interview in which they take part. All trial participants will be asked to take part in a baseline interview and then subsequent interviews 3 and 6 months later. About 20% will be asked to take part in semi-structured interviews following course completion. Thus, the maximum payment for any participant would be \$160.00 and tax information will not be required. If participants withdraw early, they will only receive payment for interviews that they participated in.

18. Data Analysis, Management and Confidentiality

All data entry screens are set up in Research Electronic Data Capture (REDCap) and, where possible, include data delimiters (i.e., skip patterns, valid range limits) to ensure correctness and minimize missing data. Data will be exported into SPSS monthly, and syntax run for cleaning, further data verification and file concatenation. Descriptive statistics will be computed through SPSS v 24 to examine participant characteristics. In preliminary analyses, descriptive statistics and frequency distributions will be examined to identify outliers and ensure integrity of merged files.

Descriptive statistics and frequency distributions will be examined to identify outliers and ensure integrity of all data. For all multi-item scales, internal consistency will be examined using Cronbach's alpha and associated statistics (e.g., item-total correlations, alpha if item deleted). To determine the feasibility of collecting data on caregiving well-being measures for a subsequent clinical trial, preliminary analyses will examine baseline differences among completers and non-completers using 2-group comparison tests (t-tests and non-parametric equivalent tests for

Page 14 of 32 Version: 1_05/05/2023

continuous variables (normally or non-normally distributed) and Chi-Square tests for categorical variables). The association of predisposing factors (demographics, caregiver history, relationship and care recipient status at baseline) with changes in outcomes over time will be examined to identify potential covariates. Where significant associations with baseline measures are detected, these potential confounders will be controlled for in subsequent analyses using covariate model adjustments. We will use multilevel longitudinal modeling analysis to test for significant changes over the 3 time points from baseline to 2- and 12-weeks post course completion.

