Sample size and power: Given an expected final sample size of 36 (assuming 10% attrition to reduce threats to validity)⁴⁹ with data completed at the 3 time points, we will be powered at 80% power and 5% level of significance to detect a large effect size (Cohen's f = 0.53) for changes from baseline.

The study team for this study will be comprised of the principal Investigators, study coordinators, and co investigators/research assistants. The coordinator and co-investigators will be responsible for the day-to-day operations of the study including recruitment and data collection management and analysis. The administrative site will be at Emory University, Nell Hodgson Woodruff School of Nursing. All team members have completed CITI training. Study-specific training for staff who will be obtaining data by interview.

[name] is the primary individual charged with identification and reporting of all adverse events (AE) and serious adverse events (SAE). [name] will provide systematic routine monitoring for the following central elements: protocol eligibility (direct source documentation of eligibility as defined in the protocol), appropriateness of consent documentation, and timeliness and accuracy of data. Monitoring reports will be conducted on a bi-weekly basis and as needed and will be reviewed at the weekly core team meeting of the investigator team.

All caregiver survey assessment data will be audited upon completion of the study. Each audit will consist of review and evaluation of 1) conformance with informed consent requirements; and 2) individual subject case review to detect low data quality (e.g., inconsistent responses on a data element that should be the same throughout the study period, such as age within 1 year). All data that impact on the interpretation of primary study endpoints will be verified with source documents. Investigator compliance with the protocol also will be evaluated. We will encourage a culture of transparency to encourage self-report of protocol breaches.

19. Provisions to Monitor the Data to Ensure the Safety of Participants

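### Feasibility of data collection is to be judged by completer versus non-completer baseline tests, which do not measure it; no retention or completeness estimate with uncertainty is named

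*Combined protocol and SAP*

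**What the plan says.** The Data Analysis Plan in Section 6 gives the purpose as "To determine the feasibility of collecting data on caregiving well-being measures for a subsequent clinical trial". The method named for it is that "preliminary analyses will examine baseline differences among completers and non-completers using 2-group comparison tests": t-tests or non-parametric equivalents for continuous variables and "Chi-Square tests for categorical variables". Section 18 repeats both purpose and method.

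The enrolment target in Section 6 is "we will recruit 40 Black caregivers in four cohorts of 10 each to participate in the prototype test". The power statement, in Section 6 and again in Section 18, reads "Given an expected final sample size of 36 (assuming 10% attrition to reduce threats to validity"), "with data completed at the 3 time points". Attrition appears there as a planning assumption, not as something to be estimated.

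Other quantitative work is given other purposes. In the same paragraph, "Descriptive statistics and frequency distributions will be examined to identify outliers and ensure integrity of all data"; Section 18 adds a description of participant characteristics. Section 6, Data Collection & Management, says that "Upon completion of each cohort data-gathering point, all data will be merged for scale computation, aggregation, and analysis". Neither place names a retention rate, a visit-completion rate, a measure of scale completeness or a confidence interval. 'Completer' is not defined.

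**The concern.** Feasibility is part of the primary objective (Section 1) and of Aim 2 (Section 2), and the plan says this analysis serves a subsequent trial. For that purpose one needs to know what share of enrolled caregivers gave data at each visit, and how precisely that share is known. A baseline comparison of those kept with those lost answers a different question: any p-value from it is compatible with 95% retention or with 60%.

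The comparison is a reasonable look at selective dropout, but the expected split is very uneven. A non-significant result from so few non-completers could easily be read as reassurance that it cannot give. What is at stake is a feasibility conclusion reached without the measure that bears on it.

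**Working it through.** **Inputs from the plan.** 40 enrolled; 10% attrition; 36 expected with data at all three time points.

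**Assumptions, none stated in the plan for this comparison.** Completer means data at all three time points; tests are two-sided at 5%; baseline differences of 0.5 and 0.8 SD are illustrative.

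**1. The plan's own figure.** 40 × (1 − 0.10) = 36, as stated, so 40 − 36 = 4 non-completers are expected. If dropout is truly 10%, the count is Binomial(40, 0.1), with 2.5% and 97.5% quantiles of 1 and 8. The chance of only 0 or 1 non-completers is 0.015 + 0.066 = 0.080.

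**2. Power of the t-test.** For k non-completers, the non-centrality is d × √[(40 − k)k/40] with 38 df. At k = 4 and d = 0.8 it is 0.8 × √(36 × 4/40) = 1.52, against a critical value of 2.02. The interval half-width for a standardized difference is approximately 2.02 × √[1/(40 − k) + 1/k].

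| Non-completers | Power, 0.5 SD | Power, 0.8 SD | Difference for 80% power | 95% CI half-width |
|---|---|---|---|---|
| 1 | 8% | 12% | 2.91 SD | 2.05 SD |
| 2 | 10% | 19% | 2.09 SD | 1.47 SD |
| 4 | 15% | 32% | 1.52 SD | 1.07 SD |
| 6 | 20% | 42% | 1.27 SD | 0.90 SD |
| 8 | 23% | 50% | 1.14 SD | 0.80 SD |

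Averaged over the binomial count (zero non-completers counted as no detection), power is 15% at 0.5 SD and 31% at 0.8 SD. At the expected split, a true 0.8 SD difference is missed 1 − 0.316 = 68% of the time.

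**3. The chi-square test.** In any 2×2 table with 4 non-completers, the two expected non-completer counts sum to 4, so both are below 5. For the planned sex mix in Section 12 (32 of 40 female) they are 32 × 4/40 = 3.2 and 8 × 4/40 = 0.8. The exact size of the uncorrected test at a nominal 5% comes from the hypergeometric distribution, for factors held by 4 to 20 of the 40:

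- It runs from 0.8% (13 of 40) to 10.8% (19 of 40).
- It exceeds 5% at 6 of the 17 margins: 5, 6, 11, 12, 19 and 20 of 40.
- At the sex margin, 8 of 40, it is 2.0%.
- Fisher's exact test runs from 0% (20 of 40) to 4.3% (4 of 40).

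**4. What a direct measure would give.** Exact (Clopper-Pearson) 95% intervals:

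- 36/40 = 90%: 76.3% to 97.2%, 20.9 points wide.
- 32/40 = 80%: 64.4% to 90.9%, 26.6 points wide.

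**5. Search for the measure elsewhere.** Canvas monitoring follows course behavior. The qualitative interviews address the course and its design. REDCap limits reduce missing entries but do not report them. None is a retention or completeness estimate.

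**The case against.** The strongest reply is that little turns on this. Participants must be sorted into completers and non-completers before they can be compared, so the retention count appears anyway and its interval can be computed later without loss. The plan calls the comparison preliminary, attaches no decision to it, and nowhere says that non-significance would show feasibility. All of that is true and limits the severity. It does not make the named method answer the stated question, nor commit the team to reporting the measure that would.

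The undefined word also matters. 'Completer' could mean someone who finished the course, in which case the 10% attrition figure does not give the count and the 36 versus 4 split loses its anchor. Data at all three time points is the natural reading because the 36 rests on it, but the plan should say so. The denominator needs the same care: Section 6 takes consent and baseline data before course enrolment, so losses in that gap could fall outside a count of those enrolled.

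The chi-square point is secondary. The test is conservative at 11 of the 17 margins examined, including the only margin the protocol plans, sex. Finally, retention from 40 people will be imprecise whatever is written. That is a limit of the sample size and a reason to show the interval.

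**Conclusion.** The concern holds. The analysis tied to data-collection feasibility measures possible selection among those lost, not how many stay or how complete their data are, and no other part of the plan names a measure that does. This part rests on the text alone and needs no assumed effect size.

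The low power is a further weakness, conditional on the two-sided 5% test, the illustrative differences and the three-time-point reading of completer. Even at 8 non-completers, the upper end of the plausible range at 10% dropout, power for 0.8 SD reaches only 50%.

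The change should be made, but the consequence is an unsupported feasibility statement, not a biased efficacy result or lost data.

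**What to change.** In the Data Analysis Plan of Section 6 and in the matching text of Section 18:

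1. Make retention at each visit and three-visit data completeness the measures of data-collection feasibility, over all 40 enrolled with exact 95% intervals. State whether the 40 are counted from baseline or from course start.
2. Define a completer in one line as a participant with data at all three time points, consistent with the 36.
3. Report completer versus non-completer baseline differences descriptively, as standardized differences with intervals. Say that non-significance will not be read as absence of selective dropout. With 0 or 1 non-completers, describe only.
4. If a p-value is given for a categorical factor, use Fisher's exact test in place of chi-square.

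The cost is wording in two sections and one extra table from data already in REDCap. The downsides are that the retention intervals will be about 21 to 27 points wide at 90% and 80% retention, that Fisher's test is conservative, and that the descriptive differences add no information on selective dropout; they only show how little there is.

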- Individuals who are not able to clearly understand English

Community Participation

We will have participation from four community partners for this study. Community partners will consist of groups that serve and support caregivers. They will meet with the research team monthly to advise on the design of the course/study. Research status updates and preliminary results will also be shared with community partners.

Page 11 of 32 Version: 1_05/05/2023

Our study is focused on one race and ethnicity, Black/African American. For the purposes of this research, the following definitions will be used for race and ethnicity. If your research questions involve race and/or ethnicity, please clarify the following:

- Race: any one of the groups that humans are often divided into based on physical traits regarded as common among people of shared ancestry. Race categories generally reflect social definitions in the US and are not an attempt to define race biologically, anthropologically, or genetically.
- Ethnicity: Shared culture, such as language, ancestry, practices, and beliefs.

For the purposes of this research, participants will be asked to identify their race and/ethnicity in this study. Only those individuals identifying as Black and/or African American will be included in this study.

This research does not involve individual who are vulnerable to coercion or undue influence.

12. Local Number of Participants

We plan to recruit 40 participants for the course. All participants will be recruited from networks around the United States. All will be African American with a goal of 32 identifying as female.

13. Recruitment Methods

The investigative team will draw on their multiple involvements and established national networks as recruitment sources to enroll a representative group of Black caregivers. PI [name]'s established community advisory board and ongoing work with Black faith communities and organizations will enable broad recruitment possibilities. Co-I [name]'s clinic has patient panel of >600, more than 40% of whom are Black Americans. Established partnerships with Black community and civic organizations will also be used.

Eligibility Determination

Screening will be conducted by distance means (phone or videoconference) by study team members.

- Is the potential subject providing care for a family member or friend? If so:
 - Does that person have a diagnosis of dementia or exhibiting signs of memory loss/cognitive impairment?

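### Chi-square is the only test named for categorical completer versus non-completer comparisons, but about 4 expected non-completers make its p-value unreliable in individual tables

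*Combined protocol and SAP*

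**What the plan says.** The Data Analysis Plan in Section 6 states that "preliminary analyses will examine baseline differences among completers and non-completers using 2-group comparison tests". Continuous variables get t-tests, or a non-parametric equivalent when they are not normally distributed. For categorical variables only one method is named: "for continuous variables (normally or non-normally distributed) and Chi-Square tests for categorical variables". Section 18 repeats it: "continuous variables (normally or non-normally distributed) and Chi-Square tests for categorical variables". Neither section mentions an exact test, a continuity correction or a rule for sparse tables.

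The numbers come from three places:

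- Section 6, Aim 2: "we will recruit 40 Black caregivers in four cohorts of 10 each".
- Sections 6 and 18, on sample size: "Given an expected final sample size of 36 (assuming 10% attrition to reduce threats to validity".
- Section 12, the only planned categorical split in the document: "All will be African American with a goal of 32 identifying as female".

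The stated purpose of the comparison is to judge whether the well-being measures can feasibly be collected in a later trial. No significance level is set for it; the 5% level appears only in the power statement for the outcome model.

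**The concern.** Pearson's chi-square test relies on a large-sample approximation that is usually trusted only when expected counts are about 5 or more. With about 4 people in one of the two groups, that condition cannot be met for any characteristic. The resulting p-value can then be well below the exact one. Two dropouts who share a trait could look like a statistically significant sign of selective loss when the exact probability of such a table is about 1 in 10. Anyone reading those p-values to judge who is lost from this kind of course could be misled in either direction, because the error rate depends on how many caregivers happen to have the trait.

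**Working it through.** **1. The plan's own figure.** 40 x (1 - 0.10) = 36 completers, so 40 - 36 = 4 expected non-completers. The 36 also fits the stated power: for three repeated measures, a noncentral F with 2 and 70 degrees of freedom and noncentrality 36 x 0.53^2 = 10.1 gives power 0.802.

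**2. Expected counts.** If m of the 40 caregivers have a characteristic, the two expected counts among non-completers are 4m/40 and 4(40 - m)/40. They sum to 4, so both are below 4. With more categories they still sum to 4, so at least half of all cells in any table are below 5. For sex, with 8 caregivers not female, the counts are 4 x 8/40 = 0.8 and 4 x 32/40 = 3.2.

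**3. Error rate for a given m.** Let a be the number of non-completers with the characteristic. If completion is unrelated to it,

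P(a) = C(m, a) x C(40 - m, 4 - a) / C(40, 4).

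Write the 2x2 table as a, b = 4 - a, c = m - a, d = 36 - c. The uncorrected statistic is

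X² = 40(ad - bc)² / [4 x 36 x m x (40 - m)],

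and the test rejects at X² ≥ 3.841, taking 5% as the level. The size is the sum of P(a) over the rejecting tables.

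| m of 40 | Pearson | Fisher |
|---|---|---|
| 2 | 0.8% | 0.8% |
| 4 | 4.3% | 4.3% |
| 5 | 6.9% | 0.4% |
| 6 | 10.0% | 0.8% |
| 8 (planned sex split) | 2.0% | 2.0% |
| 10 | 4.2% | 4.2% |
| 11 | 5.6% | 0.4% |
| 12 | 7.3% | 0.5% |
| 13 | 0.8% | 0.8% |
| 19 | 10.8% | 4.2% |
| 20 | 10.6% | 0% |

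Over m = 2 to 38 the Pearson size runs from 0.8% to 10.8%. Of the 19 margins from 2 to 20, six exceed 5% (5, 6, 11, 12, 19, 20). At the other 13 the size is 0.8% to 4.3%, and the two tests reach the same 5% decision in every possible table. A trait held by a single caregiver (m = 1) gives 10.0% for Pearson and 0% for Fisher. Fisher's size never exceeds 4.3%.

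**4. Tables where the decision changes.**

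- 2 of 4 against 4 of 36 (m = 6): ad - bc = 2 x 32 - 2 x 4 = 56. X² = 40 x 56² / (4 x 36 x 6 x 34) = 125,440 / 29,376 = 4.27, so p = 0.039. The Fisher p-value is P(2) + P(3) + P(4) = 0.0921 + 0.0074 + 0.0002, or 0.100.
- 1 of 4 against 0 of 36 (m = 1): X² = 40 x 36² / (4 x 36 x 1 x 39) = 51,840 / 5,616 = 9.23, so p = 0.0024. The Fisher p-value is 4/40 = 0.100.

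**5. Average over m.** Weighting each size by the binomial probability of m, with prevalence from 5% to 50%, gives about 3.4% to 5.5% for Pearson and 1.0% to 2.5% for Fisher.

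**6. Sensitivity to the assumptions.** With exactly 3, 5 or 8 non-completers, the largest conditional Pearson size is 14.6%, 12.5% or 20%. For three-category tables with 4 against 36, the conditional size runs from 0.7% to 19.2%. With Yates' correction in the 2x2 case it is 0% to 3.0%.

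**The case against.** The case for leaving the text alone has real force.

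- **Average error is near nominal.** A reader might infer from the 0.8% to 10.8% range that the test's true error rate is as high as 11%. That holds only for particular margins of an uncorrected 2x2 test. Averaged over margins, the test is close to nominal or slightly conservative. This stands, and it limits the point to individual tables.
- **The documented example is harmless.** At the planned sex split, chi-square and Fisher agree on every table at 5%, despite an expected count of 0.8. This stands too: a failed expected-count rule does not always mean a wrong error rate.
- **The plan did not overlook small samples for one type of variable only.** A reader might infer that it protects continuous variables against small samples and forgets categorical ones. The text ties the non-parametric option to non-normality, so that contrast is not there.
- **No consequence is written in.** A reader might infer that chance imbalances will be reported as selective attrition and carried into the next trial. The documents set no significance level or decision rule for this comparison. Covariate adjustment depends on a separate step, the association of predisposing factors with change in outcomes.
- **Fisher costs sensitivity.** Its average size of 1.0% to 2.5% makes real differences harder to detect in a comparison that already has little power. This stands, and is why the p-value should not carry the conclusion.

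None of this supports chi-square as the only named method when a table such as 2 of 4 against 4 of 36 gives 0.039 or 0.100 depending on the test.

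**Conclusion.** The point holds, with low impact. On the plan's own figures, every categorical table in this comparison breaks the expected-count condition, and the p-value of an individual table can be misleading. The documents do not support saying that the test is generally anti-conservative, or that it fails at every margin.

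The figures assume exactly 4 non-completers (an expectation, not a fixed number), a 5% level borrowed from the power statement, and no continuity correction. Step 6 shows how the range moves when the first and last of these change. No efficacy result depends on this comparison.

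Low power is the larger limit and no choice of test removes it. For a continuous variable, the standardised difference detectable with 80% power at 4 against 36 is about 2.80 x sqrt(1/4 + 1/36) = 1.5.

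**What to change.** In Sections 6 and 18, state three things:

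1. Categorical comparisons with any expected count below 5 use Fisher's exact test, or Fisher-Freeman-Halton for more than two categories.
2. Counts and percentages in each group are shown beside every p-value.
3. The comparison is descriptive, and a non-significant result is not taken to show that attrition is non-selective.

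This is a short wording change in two places. It does not touch design, sample size, data collection or the outcome model. The cost is the exact test's conservatism, which showing the counts and reading the comparison descriptively largely offsets.

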Abbreviations/ Definitions	CES-D: Center for Epidemiological Studies-Depression
	PI: Principal investigator
	HLQ: Health Literacy Questionnaire
	CWB: Caregiving while Black
	LIVE: Learning in vital engagement
	NIA: National Institute on Aging
Funding Source (if any)	National Institute on Aging (pending)

2. Objectives

The proposed psychoeducation course, *Caregiving while Black-LIVE* (Learning In Vital Engagement), seeks to equip and empower Black dementia caregivers with the knowledge, skills, and sense of mastery they need to address and cope effectively within their role broadly, not just in the context of the pandemic. The course, tailored and responsive to the needs of Black dementia caregivers, will be offered to these caregivers in a small cohort format (8-10 caregivers) in which online synchronous (facilitator-guided, face-to-face) sessions augment and complement asynchronous (self-paced) interactive components. Video instruction, resource links, and interactive exercises will promote active and engaged learning and interactivity among cohort members.

We seek to strengthen caregiving self-efficacy in Black caregivers while acknowledging the social and cultural realities of this historically minoritized racial and ethnic group. Our premise, based on Social Cognitive Theory^{14,15} and the Sociocultural Stress and Coping Model¹⁶, is that our psychoeducational course will enable Black caregivers to understand the racial disparities and inequities that substantially affect their caregiving challenges, acquire self-assessed competence in handling these challenges, and deploy effective, problem-focused coping strategies to address them, all of which, in turn, will lessen emotional distress. We propose the following aims:

Aim 1. Using an iterative, user-centered design approach, reconfigure the *Caregiving while Black* asynchronous program into a manualized and substantially more interactive online synchronous (facilitator-guided, face-to-face) and asynchronous (self-paced) interactive psychoeducation course, Caregiving while Black-LIVE.

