Aim 2. Assess the feasibility, usability, acceptability, and preliminary efficacy of the *Caregiving while Black-LIVE* course, employing a mixed-methods pre-post no control design to gather formative and evaluative data from four cohorts (n=10 each) of Black caregivers. We will employ established instruments to gather baseline and immediate post-course data on caregiving mastery, health literacy, and emotional well-being (i.e., stress, anxiety, and burden).

Exploratory Aim. Determine sustained effects in engaging in *Caregiving while Black-LIVE* by collecting data 3 months after course completion.

3. Background

Disparities for Black Caregivers. Recently heightened racial tensions, pandemic-related longer days of caregiving, shuttering of community-based care alternatives, and the ongoing challenge of navigating persistent race- and class-based disparities in the healthcare system underscore and add to the challenging and multifaceted roles Black family caregivers normally play. ^{18,19} Black caregivers typically deal with the complexities of caregiving through the lens of race and health disparities. ^{2,3,13} Prior work by PI [name] found that Black dementia caregivers felt that the health system they experience is "broken," that being "a person of color" contributed to their difficulties navigating the health system, and being dismissed by providers ¹⁸ Due to the centuries-old disadvantaged social history of Black Americans, a number of unique stressors, vulnerabilities, but also resources, have emerged which could inform and affect Black caregivers' experiences and well-being. ²⁻⁵

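### Is the detectable effect of Cohen's f = 0.53 wrong for one group of 36 caregivers measured three times?

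*Combined protocol and SAP*

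**What the plan says.** The power statement appears twice in nearly identical form, in Section 6 (Data Analysis Plan) and Section 18 (Sample size and power). It starts from the completers, "Given an expected final sample size of 36 (assuming 10% attrition to reduce threats to validity"), adds "with data completed at the 3 time points", and concludes that the study is "powered at 80% power and 5% level of significance to detect a large effect size (Cohen's f = 0.53) for changes from baseline".

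The sentence just before it, in both sections, names the analysis: a multilevel longitudinal model to "test for significant changes over the 3 time points from baseline to 2- and 12-weeks post course completion". The design is a "mixed-methods pre-post no control design to gather formative and evaluative data from four cohorts (n=10 each"), and Section 6 plans to "recruit 40 Black caregivers in four cohorts of 10 each to participate in the prototype test".

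The power statement does not define f, choose one of the outcome scales listed in Section 6, mention sphericity, or say whether the four cohorts are treated as independent of the outcome.

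**The concern.** Cohen's f is commonly read as the standard deviation of the group or time means divided by the outcome standard deviation. On that reading 0.53 is too large for 36 people each measured three times, because repeated measures make a much smaller f detectable. The stated value would then mean that the study can see only shifts of 1.12 to 1.30 outcome standard deviations, when it could see roughly half that or less. No admissible within-person correlation would reconcile the figure with the design, so it looks like an arithmetic error.

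The omissions add to the doubt. Several outcomes are collected and none is attached to the figure. Participants also learn together in groups, with course material that "will promote active and engaged learning and interactivity among cohort members", yet no allowance for cohort appears. This is the only statement of what the study can detect, so an error would mislead anyone using it to interpret the preliminary-efficacy results.

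**Working it through.** **Inputs from the plan.** 40 recruited and 10% attrition, so 40 × 0.9 = 36 analysed; m = 3 time points; one group; alpha 5%; power 80%.

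**Assumed, not in the plan.** Sphericity, independent participants, and the within-person correlation ρ wherever one is used.

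**Step 1: reproduce the stated figure.** The test of time has 3 − 1 = 2 and (36 − 1) × 2 = 70 degrees of freedom. The noncentral F distribution reaches 80% power at λ = 10.059. With λ = N × f²:

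- f = √(10.059 / 36) = 0.529, which rounds to 0.53.
- At f = 0.53, λ = 36 × 0.2809 = 10.11 and power is 80.2%.
- With 35 people (2 and 68 degrees of freedom), power is 79.0%.

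So 36 is the smallest number that gives 80% power at 0.53.

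**Step 2: the other reading.** If f is the SD of the time means over the outcome SD, then λ = N × m × f² / (1 − ρ), and the detectable value is f = √(10.059 × (1 − ρ) / 108).

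| Assumed ρ | Detectable f (SD of means / outcome SD) |
|---|---|
| −0.5 (lowest possible for three equally correlated visits) | 0.37 |
| 0 | 0.31 |
| 0.5 | 0.22 |
| 0.8 | 0.14 |

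Reaching 0.53 would need ρ = 1 − 108 × 0.2809 / 10.059 = −2.02, which is impossible. At ρ = 0, an f of 0.53 on this scale would have 99.9% power. This definition is therefore not the one behind the figure.

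**Step 3: are the two readings in conflict?** Equating the two expressions for λ, an index of 0.53 from Step 1 equals 0.53 × √((1 − ρ) / 3) on the Step 2 scale: 0.306, 0.216 and 0.137 at ρ = 0, 0.5 and 0.8. These match the table to within rounding of 0.529 to 0.53. It is one effect in two units.

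**Step 4: what 0.53 means as a change.** On the Step 1 scale, f² is the sum of squared deviations of the time means divided by σ²(1 − ρ), and a change score has SD σ√(2(1 − ρ)).

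- Rise d by the first follow-up, then held: the squared deviations sum to 2d²/3, so d = 0.53 × √3 / 2 = 0.46 change-score SDs.
- Equal steps to a total of d: they sum to d²/2, so d = 0.53 change-score SDs.

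Neither needs ρ. At ρ = 0.5 the change-score SD equals the outcome SD, so these are also 0.46 to 0.53 outcome SDs. The 1.12 to 1.30 figure (0.53 × 3/√2 and 0.53 × √6) arises only under the Step 2 definition.

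**Step 5: other routes.** A paired standardised change at alpha 0.025 gives 0.533 (power 79.5% at 0.53). A multivariate F test gives 0.541, three independent groups totalling 36 give 0.542, and a sums-of-squares form with λ = (N − 1)(m − 1)f² gives 0.38. The Step 1 route is the closest match and fits the design described.

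**The case for a change.** The best case for a change is that the reader has to work all this out. The sentence calls 0.53 large without saying on what scale, and readers using the two definitions could differ by a factor of about 2.5 (1.12 against 0.46 outcome SDs at an assumed correlation of 0.5). Several routes land near 0.53, so the text alone does not prove which was used.

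The 80% also rests on unstated conditions. With 9 completers per cohort and assumed intracluster correlations of 0.01, 0.05 and 0.10, the design effect 1 + 8 × ICC is 1.08, 1.40 and 1.80, and power at 0.53 falls to about 77%, 65% and 54%. With an assumed sphericity epsilon of 0.75 or 0.5, power is 71% or 59%.

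The reporting gap stands: the definition, outcome and assumptions are not written down, and the word large should not be read against benchmarks for the SD-of-means f. The charge of an incorrect number does not stand, because it depends on giving f a definition the plan never states. The clustering and sphericity figures are illustrations from values the plan does not contain; they show that the 80% is conditional, not that it was miscalculated.

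**Conclusion.** The figure holds as a within-person index for the 2-degree-of-freedom time test: 0.529 against a stated 0.53, and 80.2% power with 36 people, given sphericity and independent participants. That this was the authors' formula is an inference from the close match.

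What remains is an under-described sentence. A statistician can fill it in sensibly, since the sentence before it names the model and the three time points. Stating the definition would not alter the 40 recruited, the 36 expected to complete, the data collected or the analysis, and nothing in the plan makes a decision depend on 0.53. Following the plan as written would give the same results and conclusions, so no change is called for. Anyone citing the figure should read it as about 0.46 to 0.53 change-score SDs, depending on the shape of the change, and as optimistic if outcomes cluster by cohort.
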